4.3.3 Choice of chemotherapy regimen as backbone treatment

No single-agent induction chemotherapy regimen has proven superior in obtaining response in high-risk NB. Therefore, induction and consolidation regimens employ intensive multi-agent chemotherapy including platinum and alkylating agents, as well as topoisomerase-inhibitors, most often followed by surgical resection, high-dose chemotherapy with autologous cell rescue and radiation therapy (RT)⁶.

When the induction chemotherapy regimen fails, an alternative approach to second line therapy is needed. No SoC currently exists for the treatment of patients with primary refractory or first relapse of high-risk NB.

Irinotecan and temozolomide (IT) are widely used as salvage chemotherapy supported by clinical trials data.

Wagner et al assessed the effect of IT treatment in a small phase 1 study including 12 evaluable heavily pretreated patients with refractory solid tumors (incl 2 patients with NB). Oral temozolomide at 100 mg/m²/day for 5 days and IV irinotecan at either 10 mg/m²/day (n = 6) or 15 mg/m²/day (n = 6) was given daily for 5 days for 2 consecutive weeks. Median number of courses was 4. One patient had CR (Ewing Sarcoma (ES), dose level 1), two had PR (NB and ES at dose levels 1 and 2, respectively), and one had minor response (MR) (ES, dose level 1)¹⁶.

A phase 2, single-arm, single center study by Kushner et al, included 36 assessable heavily pre-treated patients with high-risk stage 4 refractory (N=19) or relapsed (N=17) NB¹⁷. Patients received IV irinotecan 50 mg/m²/day over 1 hour and temozolomide 150 mg/m²/day orally at Days 1-5. The median number of cycles was 5 (range 1-15). Overall, of the 36 patients assessable for response, 12 patients (33%) had disease regressions, including three patients (8%) with CR or PR, and nine patients with objective responses (i.e., less than PR). The safety profile was associated with manageable adverse effects and no unexpected toxicities.

A phase 2, multi-center, single arm study by Bagatell et al, included patients with primary refractory (25%) or first relapsed NB¹⁸. IT was administered in 6 cycles of 21 days with irinotecan given IV at 10 mg/m²/dose on Days 1-5 and 8-12 and temozolomide orally at 100 mg/m²/dose on Days 1-5. Of the 55 evaluable patients, 28 (stratum 1) had measurable disease by cross-sectional imaging and 27 (stratum 2) had disease only assessable by BM aspirate/biopsy or metaiodobenzylguanidine (MIBG) scan. The objective response rate was 15% overall, 11% on stratum 1, and 19% on stratum 2. Furthermore, 50% on stratum 1 and 56% on stratum 2 had stable disease (SD). Two-year event-free survival (EFS) and OS rates in the overall cohort were 13% \pm 9% and 30% \pm 10%, respectively. IT therapy was generally well tolerated and with acceptable AEs: Less

than 6% of patients experienced > Grade 3 diarrhea. Although > Grade 3 neutropenia was observed, less than 10% of patients developed evidence of infection while neutropenic.

Finally, in the BEACON study in patients with high-risk refractory/relapsed NB, temozolomide was administered at 100mg/m²/day orally and irinotecan at 50mg/m²/day IV on Days 1 to 5 of a 3-week cycle, for 6 cycles or until progression (NCT02308527). With a median follow-up time of 15.4 months, irinotecan + temozolomide ± bevacizumab (N=60) vs. temozolomide ± bevacizumab (N=61) improved PFS and OS: Hazard ratios of 0.66 [95%CI 0.43-1.00] and 0.63 [95%CI 0.41-0.99], respectively¹⁹.

Based on the above data, IT will serve as backbone chemotherapy in Trial 203.

4.3.4 Combining naxitamab with irinotecan and temozolomide

Although IT therapy may result in disease stabilization in patients with primary refractory or first relapse of NB, response rates remain relatively low with CR rates of 5-10%^{17, 18}. To improve the outcome for these patients, the IT regimen could serve as a backbone on which mAb targeting GD2 is added. Although IT have known myelosuppressive adverse effects, anti-GD2 mAb therapy may be effective in this IT chemotherapy setting when combined with GM-CSF; ADCC and CDC are dependent on complement and myeloid cells such as neutrophils, which recover faster than lymphocytes²⁰.

In support of these considerations, a significant and early anti-tumor activity was observed in a small, randomized phase II trial by Mody et al. with dinutuximab + GM-CSF vs temsirolimus both as add-on to IT therapy in patients with primary refractory or first relapse of NB. All patients received oral temozolomide (100 mg/m²/dose) and IV irinotecan (50 mg/m²/dose given over 90 min) on Days 1–5. Treatments were repeated in cycles of 21 days. Median number of treatment courses were 3 [interquartile range (IQR) 2–10] and 6 [IQR 3–17] in the temsirolimus and dinutuximab arm, respectively. Of the 17 patients randomized to IT + dinutuximab, 9 (53%, 95% CI: [29.2%, 76.7%]) had objective response (OR)(5 CR, 4 PR.). In the temsirolimus arm, 1 PR was observed (5.6%, 95% CI: [0.0%, 16.1%]). These responses appeared to be irrespective of disease status (relapsed vs. refractory disease, measurable vs. evaluable disease)²¹. A follow-up study including additional 36 patients non-randomly assigned to IT + dinutuximab + GM-CSF confirmed the favorable results. Of 53 patients overall, 22 had OR (41.5%, 95% CI: [28.2%, 54.87%]; 11 CR, 11 PR) and 22 patients had SD²². This IT dosing regimen has been applied as backbone therapy with median number of cycles around 4 in several other NB clinical trial settings²³⁻²⁵.

Preliminary and promising results have also been obtained with naxitamab + GM-CSF in combination with irinotecan and temozolomide (human3F8, irinotecan, temozolomide, sargramostim; HITS). One study included 46 (23 enrolled on protocol and 23 on compassionate use basis) heavily prior-treated patients with high-risk NB refractory to induction chemotherapy (N=7) or prior relapse (N=39). Each cycle comprised of irinotecan 50 mg/m²/day IV plus temozolomide 150 mg/m²/day IV or orally (Days 1-5);

naxitamab 2.25 mg/kg/day IV over 30 minutes, Days 2, 4, 8 and 10 (total 9 mg/kg or 270 mg/m² per cycle) and GM-CSF 250 mg/m²/day sc, Days 6-10. Median age at enrollment was 6.6 years and median number of prior relapses was 2. Early responses, assessed after 2 cycles, were documented in 18 (39%) patients and were complete (N = 9), partial (N = 8), and mixed (N = 1); 13 patients had SD²⁶. Another study included 44 (36 evaluable and 8 non-evaluable) heavily prior-treated patients with NB treated with the same IT/naxitamab treatment regimen as above under compassionate use in the outpatient setting in Spain²⁷. The median number of cycles was 5 (range 1-15). Median age at enrollment was 6 years, 16 patients had high-risk NB refractory to induction chemotherapy and 28 patients had previously \geq 1 relapse (median number of prior relapses was 2). Early responses, assessed after 2 cycles, were documented in 17 (47.2%) of the 36 evaluable patients; 11 patients had CR (30.5%), and 6 patients had PR (16.7%). Ten patients had SD. One-year PFS was 37.0% (95% CI: 21.8% to 62.9%), median time to progression was 9.2 months. One-year OS was 55% (95% CI: 39.4% to 76.9%). In both studies, toxicities included myelosuppression and diarrhea as expected with IT, and pain and hypertension as expected with naxitamab. No other >Grade 2 related toxicities occurred.

In all the above studies the safety profile of the IT regimen was manageable.

Based on these data, naxitamab may have the potential to improve outcomes when used as second line therapy in combination with IT in patients with high-risk NB with primary refractory disease or first relapse. In line with the study by Mody et al., IT will be administered on Days 1 to 5 at cycles of 21 days for up to 18 cycles: irinotecan IV at 50 mg/m²/dose/day over 90 min and temozolamide orally at 100 mg/m²/dose.

4.3.5 Naxitamab dose selection and infusion rate

The efficacy and safety of naxitamab has been substantiated in Trials 12-230 and 201 at 3.0 mg/kg/infusion over a 30-minute infusion period on Days 1, 3 and 5 (9.0 mg/kg/cycle) every 28 days. In Trial 203, naxitamab will be administered in combination with GM-CSF in combination with IT in cycles of 21 days (see [4.3.4](#)). To reduce the risk of naxitamab associated AEs in this treatment regimen, a slightly slower naxitamab dosing regimen per cycle will be applied at 2.25 mg/kg/day on Days 2, 4, 8 and 10 (total 9 mg/kg per cycle) as described by Mora J et al. (see Section [4.3.4](#))^{26,27}. Furthermore, to reduce the risk of infusion related toxicity, naxitamab will be administered over minimum 60 min for the first infusion and 30 min for subsequent infusions.

If patients discontinue IT treatment due to toxicity, the naxitamab+GM-CSF regimen can be continued: naxitamab will then be administered IV at 3.0 mg/kg/day on Days 1, 3 and 5 (9.0 mg/kg/cycle) in cycles of 28 days in accordance with the regimen applied in the naxitamab clinical development program (see Section [4.3.2](#)).

4.3.6 Use of GM-CSF in combination with naxitamab

During the naxitamab clinical development program, naxitamab has been administered in combination with GM-CSF (sargramostim) (see Section [4.3.2](#)). Furthermore, naxitamab

is approved for combination treatment with GM-CSF in the US and dinutuximab (Unituxin®) is approved for use in combination with IL-2 and GM-CSF in the US^{12, 13}. In the clinical setting, GM-CSF increases neutrophil production and maturation of monocytes to macrophages and can amplify the anti-NB activity of naxitamab via effects on these cells^{28, 29}. Moreover, GM-CSF has been found to be well tolerated compared to other cytokines such as interleukin-2 (IL-2)^{26, 27}. Based on these considerations, naxitamab will be administered in combination with GM-CSF in this trial. GM-CSF (sargramostim) will be administered at 250 ug/m²/day sc on Days 6-10, in accordance with a dosing regimen found to be efficacious and with a manageable safety profile^{11, 29, 30} and in an ongoing clinical trial at MSK (NCT03189706). If patients discontinue IT treatment due to toxicity, the naxitamab+GM-CSF regimen can be continued: GM-CSF will be administered sc at 250 ug/m²/day on Days -4 to 0 and at 500 ug/m²/day on Days 1 to 5 in cycles of 28 days in accordance with the regimen applied in the naxitamab clinical development program.

4.3.7 Choice of trial population

The trial will include patients with high-risk NB with measurable and/or evaluable disease and either with primary refractory disease or in first relapse following induction and consolidation therapy. Primary refractory disease or first relapse following induction therapy is associated with poor outcomes and no approved SoC exists for treatment of this patient population. Thus, there is a high unmet medical need for more efficacious treatments. The age cut-off of 12 months is applied, as most infants with disseminated disease have a favorable outcome following treatment with chemotherapy and surgery³¹⁻³³.

4.3.8 Choice of trial design

Trial 203 is an open label, uncontrolled, multicenter trial. Due to the devastating nature of refractory and relapsed high-risk NB with 10-years OS of less than 15% and the only modest effect of IT treatment alone, a single arm trial design is applied. The primary endpoint ORR is an endpoint accepted for single arm trials by regulatory authorities for efficacy evaluation of anti-cancer therapies^{34, 35}.

The assessment of the primary endpoint after completion of 4 cycles is considered appropriate based on published clinical trials on IT treatment and on completed trials on naxitamab^{17, 18, 21, 22}. The long-term follow-up of 2-years after End of Treatment is to gain data on long-term efficacy and safety of naxitamab in combination with IT.

4.4 Benefit-risk assessment

Chemo resistant and relapsed disease are major obstacles to curing high-risk NB. Despite intensive frontline therapy, approximately 50% of patients with high-risk NB experience persistence of disease or develop PD⁶. The prognosis for patients with recurrent or refractory NB is extremely poor with 10-years OS of less than 15%⁷. Thus, more efficacious treatments for this patient population remains a large unmet medical need.

Naxitamab is a mAb targeting GD2 widely expressed on NB cells. Across Trials 12-230 and 201 in patients with high-risk refractory or relapsed NB in bone and/or BM, naxitamab in combination with GM-CSF was found to provide a statistically significant and clinically relevant ORR ranging from █ to 68% and CR rates ranging from █ to 59%. In these trials, naxitamab was found to be overall well tolerated with acute toxicities/infusion related AEs that could be managed by pre-medications (opioids, corticosteroids, antipyretics, and antihistamines) along with concomitant administration of normal saline, opioids, nebulized beta-2 agonists, and oxygen as applicable. In further support of a manageable safety profile, 95% of all infusions were performed in the out-patient setting with similar rates across cycles and infusions in Trial 201. Moreover, treatment of patients with naxitamab + GM-CSF in combination with IT indicated promising anti-cancer effect also with a manageable safety profile^{26,27}.

Based on the above, naxitamab + GM-CSF in combination with IT has the potential to improve outcomes earlier during the high-risk NB disease course and thereby address the important unmet medical need in this patient population.

5 TRIAL OBJECTIVES

5.1 Primary Objective

To investigate the efficacy of naxitamab + GM-CSF in combination with IT as assessed by ORR in patients with high-risk NB with primary refractory disease or in first relapse.

5.2 Secondary Objective

To further investigate the efficacy and safety of naxitamab + GM-CSF in combination with IT in patients with high-risk NB with primary refractory disease or in first relapse.

6 ENDPOINTS

6.1 Primary Endpoint

ORR, defined as the proportion of patients obtaining a centrally assessed CR or PR according to the International Neuroblastoma Response Criteria (INRC) at or before completion of four cycles.

6.2 Secondary Endpoints

1. ORR after 2 cycles defined as the proportion of patients obtaining a centrally assessed CR or PR according to the INRC at completion of two treatment cycles
2. Duration of response (DoR), defined as the time from first centrally assessed OR (CR or PR according to the INRC) to PD or death
3. CR rate, defined as the proportion of patients obtaining a centrally assessed CR according to the INRC at or before completion of four treatment cycles
4. CR rate after two cycles defined as the proportion of patients obtaining a centrally assessed CR according to the INRC at completion of two treatment cycles
5. Minor response (MR) rate, defined as the proportion of patients obtaining a centrally assessed MR according to the INRC at or before completion of four treatment cycles
6. "MR or better" rate, defined as the proportion of patients obtaining a centrally assessed CR, PR or MR according to the INRC at or before completion of four treatment cycles
7. Proportion of patients with disease in BM at enrollment who obtain centrally assessed CR in BM and convert to minimal residual disease (MRD) negative (assessed by reverse transcriptase-quantitative polymerase chain reaction (RTqPCR)) at or before completion of four cycles
8. Time to First Subsequent Therapy or death (defined as the time from initiation of treatment with investigational medicinal products (IMP) until death or start of new anti-cancer treatment (prohibited as per protocol))
9. PFS defined as the time from first IMP administration until centrally assessed PD or death, whichever comes first
10. OS defined as the time from first IMP administration until death
11. 1- and 2-years PFS defined as the proportion of patients alive and with no centrally assessed PD at 1- and 2 year, respectively after first IMP administration
12. 1- and 2-year OS defined as the proportion of patients alive at 1- and 2 years after first IMP administration
13. Safety incl. incidence of AEs and SAEs graded according to Common Terminology Criteria for AEs (CTCAE) version 5.0
14. Pain during naxitamab infusions as assessed by Wong Baker- and FLACC scales
15. Incidence of ADA (including assessment for neutralizing potential and time to first positive ADA assessment from first day of naxitamab administration)
16. Number of naxitamab infusions done in an out-patient setting defined as infusions not requiring admission to hospital due to adverse events

6.3 Exploratory Endpoints

1. Confirmed ORR after 2 cycles defined as the proportion of patients obtaining a centrally assessed confirmed CR or PR according to the INRC at completion of two treatment cycles
2. Duration of confirmed response, defined as the time from first centrally assessed confirmed OR (CR or PR according to the INRC) to PD or death
3. Confirmed CR rate, defined as the proportion of patients obtaining a centrally assessed confirmed CR according to the INRC at or before completion of four treatment cycles
4. Confirmed CR rate after two cycles defined as the proportion of patients obtaining a centrally assessed confirmed CR according to the INRC at completion of two treatment cycles
5. Primary endpoint and secondary efficacy endpoints (number 1-7, 9 and 11) based on investigators' local assessments

7 DESCRIPTION OF DESIGN AND TRIAL POPULATION

7.1 Overall Trial Design

This is an open label, single-arm, multicenter, phase 2 trial, in patients \geq 12 months of age with high-risk NB with primary refractory disease or in first relapse. 52 patients who have all received at least 1 dose of IMP will be enrolled. Response assessment of images and BM biopsies and aspirates will undergo central review by independent external experts. An independent Data Monitoring Committee (DMC) will oversee trial safety.

7.2 Overall Trial Plan

The trial includes a screening visit to assess the patient's eligibility. Patients fulfilling the eligibility criteria will receive up to 70 weeks of treatment with naxitamab and GM-CSF in combination with IT. End of Treatment (EOT) will be 6 (up to 10) weeks after last treatment. After EOT the patient will enter a long-term FU up to 2 years. Please refer to Figure 1 in [7.2.1](#).

7.2.1 Treatment

[figure not shown]
Each treatment cycle is 21 days. Patients will receive irinotecan 50 mg/m²/day IV and temozolomide 100 mg/m²/day orally (both on Days 1-5) in combination with naxitamab 2.25 mg/kg/day IV (Days 2, 4, 8 and 10) (total 9 mg/kg per cycle), and GM-CSF 250 μ g/m²/day sc, (Days 6-10). Patients will receive up to 18 IT cycles after enrollment. Naxitamab and GM-CSF will be given for at least 8 cycles.

Patients who discontinue IT due to unacceptable toxicity will be offered treatment with naxitamab + GM-CSF alone. The treatment will be administered in 28-days cycles with naxitamab 3.0 mg/kg/infusion at Days 1, 3 and 5 and GM-CSF 250 μ g/m²/day for 5 days from Days -4 to 0, and at 500 μ g/m²/day for 5 days from Day 1 to Day 5. The total number of naxitamab treatment cycles will be at least 8 cycles (including the cycles given in the HITS regimen).

Patients who discontinue GM-CSF due to unacceptable toxicity should continue naxitamab treatment.

Patients achieving a CR or PR (both patients receiving HITS or naxitamab + GM-CSF alone) should receive 8 naxitamab cycles or 5 additional naxitamab cycles following the objective response, whichever provides the longest treatment with naxitamab. Patients who have achieved a MR or SD at completion of the 8 cycles (both patients receiving HITS or naxitamab + GM-CSF alone) may receive naxitamab + GM-CSF consolidation treatment for 5 cycles administered at every 6 weeks (in the HITS regimen) or 8 weeks (in the naxitamab + GM-CSF alone regimen). The total number naxitamab cycles to be administered includes the treatment cycles administered in the HITS regimen.

Figure 1 Trial design

*each cycle is 21 days, ** each cycle is 28 days

¹Patients achieving a CR or PR should receive at least 8 naxitamab cycles or 5 additional naxitamab cycles following the objective response, whichever provides the longest treatment with naxitamab

² Patients should receive at least 8 cycles of naxitamab + GM-CSF including the cycles in the HITS regimen

7.3 Recruitment Period

It is estimated that ~18 months will be needed to recruit the planned number of patients.

7.4 Screening/Pre-treatment Evaluation

Pre-treatment evaluations should be completed within 21 days prior to start of trial treatment on Day -3. Please refer to the screening visit in the flowchart (Section 3) Procedures (except BM biopsies/aspirates and imaging) performed by site as part of SoC within the screening period may be used for the evaluation of patient eligibility even if the evaluation is performed prior to patient information and ICF signature.

7.5 Patient Replacement

No patient replacement is allowed.

7.6 Screening Failures and Re-screening

Screen failures are defined as patients who consent to participate in the clinical trial but are not eligible according to in/exclusion criteria.

Individuals who do not meet the criteria for participation in this trial may be re-screened under the following circumstances:

- If the time elapsed since occurrence of a treatment/procedure would otherwise qualify for an exclusion criterion
- If the laboratory parameters defined in the exclusion criteria are met but are expected to improve and not meet the exclusion criteria at the discretion of the investigator.
- Age < 12 months
- Stabilization or improvement of a clinical condition that would otherwise qualify for an exclusion criterion at the discretion of the investigator

If a patient is re-screened the patient should receive a new patient identifier (ID), i.e., a patient can have multiple screening IDs, but only one treatment ID. If a patient is re-screened the parents/patient must sign a new informed consent form (ICF).

7.7 Enrollment

A patient is defined as enrolled, when the patient is confirmed eligible according to in/exclusion criteria and ready to start pre-treatment Day-3.

7.8 Follow-up

EOT assessments should take place minimum 6 weeks (up to 10 weeks) after last treatment. If treatment is discontinued due to PD, planned initiation of new anti-NB treatment prohibited as per protocol, withdrawal from the trial or investigator judges it warranted due to medical reasons/non-compliance, the patient should be called for EOT visit as soon as possible and before initiation of new anti-NB treatment. The patients should subsequently be followed for safety and new anti-cancer therapy for a total of 6 weeks after last treatment (see flowchart in Section 3 and treatment discontinuation criteria in Section 7.12).

After EOT, a long-term FU period will start. The patient will attend long-term FU visits approximately every 4 months for up to 2 years after EOT.

The investigator will perform response assessments (if the patient has not experienced PD) (see Section 3, 9.1.1, 9.1.2 and [Appendix 2](#)), report death and PD (as applicable) and collect information on SAEs ongoing at EOT visit, new SAEs at least possibly related to naxitamab treatment, secondary malignancies, and autoimmune diseases. Furthermore, new anti-cancer therapy should be collected as concomitant medication. Please refer to flowcharts in Section 3 and [Appendix 2](#).

Trial period completion is defined as when the patient has completed the final scheduled visit (long-term FU visit 2 years after EOT).

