7.12 Premature Discontinuation of Treatment

General discontinuation criteria

A patient should be discontinued from treatment with all IMPs if any of the following situations occur:

1. Grade 4 anaphylaxis related to naxitamab
2. Grade 3 anaphylaxis related to naxitamab not responding to medical intervention at the discretion of the investigator
3. Grade 4 sensory neuropathy or Grade 3 sensory neuropathy that interferes with daily activities for more than 2 weeks at the discretion of the investigator
4. CTCAE Grade 3 pain unresponsive to maximum supportive measures at the discretion of the investigator
5. Grade 4 bronchospasm
6. Grade 3 bronchospasm not responding to medical intervention at the discretion of the investigator
7. Posterior reversible encephalopathy syndrome (PRES)
8. The investigator judges it necessary for medical reasons/non-compliance
9. The patient receives prohibited therapy and/or procedures during the trial, see Section [8.4.8](#)
10. Pregnancy
11. Patient/legal guardian withdraw consent to treatment
12. PD

Discontinuation criteria for IT

A patient should be discontinued from IT treatment if any of the following situations occur:

1. If the patient experiences neutropenia that causes a delay \geq 14 days after the first dose reduction by 20% of irinotecan and the second dose reduction by 20% of temozolomide
2. If the patient experiences thrombocytopenia that causes a delay \geq 14 days after the first dose reduction by 20% of irinotecan and the second dose reduction by 20% of temozolomide
3. If the patient does not meet the criteria to start the next cycle within 21 days after the planned subsequent cycle start date
4. Recurrence of \geq Grade 3 diarrhea despite maximal use of anti-diarrheals, prophylactic antibiotics, and a dose reductions of irinotecan of 20%
5. Recurrence of \geq Grade 3 regimen-related nausea and/or vomiting despite optimization of anti-emetic drugs and a dose reduction of IT by 20%
6. If \geq Grade 3 regimen-related dehydration recurs and persists for >3 days despite a dose reduction of IT by 20%

Discontinuation criteria for GM-CSF

A patient should be discontinued from GM-CSF treatment if any of the following situations occur:

1. Injection site reactions \geq CTCAE Grade 3
2. Allergic reactions (including anaphylactic reactions) \geq CTCAE Grade 3

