8.1.4 Treatment after Discontinuation of IMP

If the patient prematurely discontinues all IMPs and after End of Trial, any treatment deemed safe and justified by the Investigator can be administered according to clinical practice and at the discretion of the Investigator.

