10.5 Adverse Event Reporting

10.5.1 Non-Serious Events

Non-serious AEs should be reported from the day of first IMP administration until 42 days after the last IMP administration. Non-serious AEs occurring between signing the ICF and the first IMP administration must be recorded as medical history.

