10.5.2 Serious Adverse Events

Serious AEs should be reported from signing the ICF until 42 days after the last IMP administration.

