12.5 Safety Analysis

The SAF will be used for the safety analyses. The overall observation period will be divided into 3 parts:

1. pre-treatment period: from day of patient's informed consent to the day before first dose of IMP
2. on-treatment period: from day of first dose of IMP to 42 days after last dose of IMP
3. post-treatment period: starting at day 43 after last dose of IMP.

If dates are incomplete in a way that clear assignment to pre-, on-, post-treatment period cannot be made, then the respective data will be assigned to the on-treatment period.

Additional analyses and presentations will be included in the SAP.

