12.5.1 Adverse events

AE data will be presented descriptively in summary tables and listings. AEs will be regarded as Treatment-Emergent AEs (TEAEs) if they occur after start of first IMP administration.

An infusion/administration related TEAE is an AE that occurs on a day of IMP administration (after start of IMP administration) and is considered related to the IMP treatment.

An infusion related hypersensitivity TEAE is an AE that match a selected list of hypersensitivity terms based on reported preferred terms (including the MedDRA SMQ narrow scopes of anaphylactic reaction, angioedema, hypersensitivity and severe cutaneous reaction), that occurs on a day of naxitamab infusion (after the infusion start) or the day after a naxitamab infusion irrespectively of relatedness to naxitamab.

AEs with onset during the pre- and post-treatment period will be listed. AEs with onset during the on-treatment period will be summarized as follows: summaries of AEs will be presented for all TEAEs, IMP-related TEAEs, CTCAE Grade 3 or higher TEAEs, IMP-related CTCAE Grade 3 or higher TEAEs, infusion/administration-related TEAEs, infusion-related hypersensitivity TEAEs, SAEs, IMP-related SAEs, CTCAE Grade 3 or higher SAEs, IMP-related CTCAE Grade 3 or higher SAEs, TEAEs leading to treatment discontinuation, AEs leading to death.

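### Adverse events that start on the next anti-cancer therapy, up to 42 days after the last IMP, are tabulated as on-treatment, so the all-causality safety tables can mix two regimens

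*Combined protocol and SAP*

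**What the plan says.** Four parts of the protocol fit together.

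- **Stopping.** Progression is one of the general criteria in Section 7.12, which opens: "A patient should be discontinued from treatment with all IMPs if any of the following situations occur".
- **Next therapy.** After all IMPs are stopped early, Section 8.1.4 says that "any treatment deemed safe and justified by the Investigator can be administered according to clinical practice". It states no waiting period. Section 7.8 expects new treatment soon: "the patient should be called for EOT visit as soon as possible and before initiation of new anti-NB treatment". It continues: "The patients should subsequently be followed for safety and new anti-cancer therapy for a total of 6 weeks after last treatment". Footnotes to the flow chart in Section 3 and to Table 12 in Appendix 2 repeat the 6-week follow-up.
- **Collection.** Section 10.5.1: "Non-serious AEs should be reported from the day of first IMP administration until 42 days after the last IMP administration". Section 10.5.2: "Serious AEs should be reported from signing the ICF until 42 days after the last IMP administration".
- **Tabulation.** Section 12.5 defines the "on-treatment period: from day of first dose of IMP to 42 days after last dose of IMP". Section 12.5.1 treats any AE after the first IMP administration as treatment-emergent, and says that "AEs with onset during the on-treatment period will be summarized as follows". The list that follows includes both all-causality and IMP-related summaries.

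For efficacy, the start of another anti-cancer therapy does change the analysis: it censors duration of response (Section 12.4.3), and PFS follows the same rule (Section 12.4.6).

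**The concern.** Safety is part of the secondary objective (Section 5.2) and a secondary endpoint (Section 6.2). The trial has one arm, so no control group shows how many events come from elsewhere. A reader of the SAE or fatal-AE table will take its contents as experience on naxitamab, GM-CSF, irinotecan and temozolomide. If some patients had already moved to another regimen when the event began, the table describes a mixture, concentrated in patients who progressed.

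The AE overviews by subgroup in Section 12.11 are exposed too. They compare refractory, first-relapse and first-progression patients. Section 4.1 cites median PFS of 12.5 months in refractory and 5.7 months in relapsed disease. Groups that progress at different rates would carry different amounts of next-regimen toxicity, so part of an apparent subgroup difference could come from the counting rule.

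**Working it through.** **Step 1: do the windows coincide?** 6 weeks × 7 = 42 days. The follow-up in Section 7.8, the reporting windows in Sections 10.5.1 and 10.5.2 and the on-treatment period in Section 12.5 therefore end together. If new therapy starts d days after the last IMP, with d below 42, then 42 − d days of follow-up on it count as on-treatment. For example, d = 14 gives 28 days and d = 21 gives 21 days. Section 12.5 also assigns AEs with unresolvable dates to the on-treatment period, which can only add to it.

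**Step 2: which tables are open to these events?**

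| Summary in Section 12.5.1 | Can an event caused by the next regimen enter? |
|---|---|
| All TEAEs; Grade 3 or higher TEAEs; SAEs; Grade 3 or higher SAEs; AEs leading to death | Yes; onset by day 42 is enough |
| IMP-related versions | Partly protected: Section 10.5.11 lets the investigator rate as not related an event explained by other therapy |
| Infusion/administration-related TEAEs | Protected: onset on an IMP day and relatedness are both required |
| Infusion-related hypersensitivity TEAEs | Protected: onset on a naxitamab infusion day or the day after |

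**Step 3: how large could it be?** The documents give neither the share who stop for progression, nor the time to next therapy, nor the toxicity of that therapy. All three inputs below are assumptions.

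- Planned treated patients: 52 (Section 7.1).
- Stop for progression: 30% to 60%.
- Of these, start new therapy by day 42: 50% to 80%.
- Of these, have an SAE on it within the window: 30% to 60%.

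Patients with mixed follow-up = 52 × share stopping × share starting:
- low: 52 × 0.30 × 0.50 = 7.8
- high: 52 × 0.60 × 0.80 = 25.0

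Patients with an SAE that starts on the next regimen:
- low: 7.8 × 0.30 = 2.3, or 4.5% of 52
- high: 25.0 × 0.60 = 15.0, or 28.8% of 52

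**Step 4: how far would a patient-level incidence move?** A patient who already had an event of that type on trial treatment is counted once. If b is the proportion who did, and the two are independent, the increase is the Step 3 percentage × (1 − b).

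- SAEs, with b = 40% assumed: 4.5 × 0.60 = 2.7 points to 28.8 × 0.60 = 17.3 points.
- Grade 3 or higher TEAEs, with b = 92%, the upper figure that Section 4.3.2 reports for earlier naxitamab trials, and the same 30% to 60% event rate: 4.5 × 0.08 = 0.4 points to 28.8 × 0.08 = 2.3 points.

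TEAE incidence close to its ceiling thus hardly moves, while SAE incidence has room to move. For AEs leading to death no earlier event of that type can mask a new one, but the documents give no basis for a figure.

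**The case against.** The strongest reply is that a single fixed 42-day window, used consistently for collection and analysis, is a legitimate choice. All-causality tables contain unrelated events by design. Ending follow-up at new therapy shortens it selectively in patients who progress, and could hide late IMP toxicity that was rated unrelated. Efficacy censoring and safety windows answer different questions, so the contrast with Sections 12.4.3 and 12.4.6 does not make the safety rule inconsistent. AEs are also listed, and concomitant medication is recorded with start dates (Section 8.4), so a split can be programmed at any time. Sections 12.5 and 12.13 leave further detail to the SAP, and the documents contain no further SAP text.

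Most of this stands. It is why the window should remain and the split be added beside it. It does not remove the point: Section 12.5 already defines the period, the text available has no split, and a table that can be programmed later is not a prespecified one.

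Three stronger readings are tempting and not supported.

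- A reader might infer a particular inflation of SAE incidence, for instance by taking one-year PFS of 37% in the cited series (Section 4.3.4) to mean that about 30 of 52 stop for progression and all soon start new therapy. That series was more heavily pretreated (median 2 prior relapses), PFS also counts deaths and progressions after treatment has ended, and the documents give no time to next therapy and no SAE rate.
- A reader might infer that only the IMP-related tables are shielded. The timing rules in Section 12.5.1 shield two more.
- A reader might infer that all the TEAE figures are materially distorted. Near the ceiling, patient-level incidence is not.

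**Conclusion.** The point holds as a gap in tabulation. The plan foresees new anti-cancer therapy inside the 42-day window and counts every event there as on-treatment, so next-regimen toxicity can enter the five all-causality summaries and the AE subgroup overviews. The same applies to the other early-stop reasons in Section 7.8, including planned new anti-neuroblastoma treatment.

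The size is not determined by the documents. The range of about 2 to 15 of 52 patients rests wholly on the assumed inputs, and its width shows how little they constrain it. The effect is probably small for patient-level TEAE incidence and larger for SAEs and fatal AEs, although some deaths soon after progression will be due to disease. The primary endpoint is unaffected. This is an inexpensive gain in interpretability, worth prespecifying before data lock.

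**What to change.** Leave AE collection and the 42-day on-treatment period as they are. In Sections 12.5 and 12.5.1, or in the SAP, add:

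1. A second version of the all-causality tables (at least SAEs, Grade 3 or higher TEAEs, AEs leading to death, and the AE subgroup overviews of Section 12.11) with follow-up ending at the earlier of day 42 and the day before the first new anti-cancer therapy. Take the definition of new therapy from Section 12.4.3, so that efficacy and safety use one date.
2. A separate table of events with onset from the start of new therapy to day 42, showing the investigator's causality assessment.
3. A nesting rule: an event with onset within the 42 days and rated IMP-related stays in both the all-TEAE and the IMP-related tables, in the truncated version too. The related tables then remain a subset, and nothing after day 42 is admitted.
4. A statement of how partial dates are placed relative to the start of new therapy.

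The cost is a few sentences and a few extra tables. New anti-cancer therapy is already followed (Section 7.8), and medication start dates are already recorded (Section 8.4), so no visit or data item is added. The downside is that a late IMP effect rated unrelated is absent from the truncated version; it stays visible in the full-window and separate tables.
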